- Medications administered	Type, dose and timing of each seizure medication during the admission and at the time of discharge home Medication duration measured as short (discontinued prior to or at discharge) vs. prolonged (discontinued after discharge)			
3-Month Follow Up (Appendix 2)				
- 1 hr outpatient EEG	Scored by 2 independent EEG reviewers, blinded to patient history			
12-18- & 24-Month Follow Ups (Appendices 3 & 4)				
- Functional neurological score	Warner Initial Developmental Evaluation of Adaptive and Functional Skills (WIDEA FS) administered by telephone			
- Epilepsy evaluation	Epilepsy assessment instrument and modified Engel classification (administered by telephone); epilepsy syndrome characteristics and treatment confirmed through medical record review			
Parent Surveys (Appendix 5)				
- Parent and family well-being measurement	A suite of validated instruments and open-ended free-text questions were selected in partnership with our Parent Partners. These will be administered at the time of hospital discharge and at the 12-month, 18-month, and 24-month follow-up.			

Selection of comparators [RQ-5]. The primary comparator will be duration of medication use for the treatment of acute symptomatic seizures.

- As described in our analysis below, we will examine duration of phenobarbital as follows:
 - Treatment as a dichotomous predictor (short versus prolonged, Aims 1 & 3)
 - Treatment as a continuous predictor (Aim 2)

Preliminary data from the *Neonatal Seizure Registry* support two main patterns of treatment, which will be our comparators:

- 1. Short duration phenobarbital: Discontinuation of phenobarbital for acute
- symptomatic neonatal seizures prior to discharge home.
- 2. Prolonged duration phenobarbital: Continuation of phenobarbital for acute symptomatic neonatal seizures until outpatient follow-up (age 2-4 months).

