according to pre-clinical studies⁴². Therefore, levetiracetam could have less impact than phenobarbital on neurodevelopmental outcomes. We will analyze the small subset of infants who are maintained on levetiracetam as a separate subgroup to obtain preliminary data regarding the impact of this medication on neurodevelopmental outcomes, epilepsy, length of stay, and parent and family well-being.

Subject recruitment. A study investigator or research coordinator will identify eligible newborns during the neonatal admission at each of the participating study sites. A study investigator will approach the parents/guardians of eligible patients and, using a consent form approved by the local Institutional Review Board, will describe the anticipated risks and benefits of the study. The consent team will include only experienced team members who are sensitive to the vulnerable nature of this population and who emphasize the voluntary nature of research. Since this study will place infants at no more than minimal risk, and could augment patient care through standard provision of the follow-up EEG, we anticipate excellent consent rates. Based on feedback from our Parent Partners, we have also attempted to minimize burden to families, and loss to follow-up, through use of a telephone-based follow-up assessment, rather than requiring in-person developmental testing.

Barriers to recruitment. Based on our extensive collective experience with long-term follow-up for neonates at risk for epilepsy – for example the PIs' NIH-supported studies (5K23HD068402, K23NS066137) and the Prevention of West Syndrome study (funded by CURE), as well as the UCSF P01NS082330-01 *Repair after Neonatal Brain Injury, which has enrolled and followed more than 750 neonates since its inception in the 1990s* – we anticipate optimal recruitment when families are approached prior to hospital discharge. Since some of the *Neonatal Seizures Registry* sites draw patients from significant geographical distances, families will be provided a stipend to off-set travel expenses associated with the follow-up EEG. The EEG will be paid for by the PCORI grant, unless the treating physician orders it on clinical grounds.

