Appendix 4: Seizure/Epilepsy Follow-Up Telephone Questionnaire (Aim 1b)

Date	
Subject #	Subject age
Person completing questionnaire	

- 1. Did your child have seizures as a newborn (at any time during the first 28 days of life)?
 - a. Yes
 - b. No
 - c. Don't know
- 2. If your child was treated with medicine for neonatal seizures, did he/she ever stop taking this medicine?
 - a. Yes, before we left the hospital
 - b. Yes, after we left the hospital
 - c. No
 - d. Don't know
- 3. Your child was treated in the hospital for his or her seizures. After you went home from that admission, did your child ever have more seizures?
 - a. Yes
 - b. No
 - c. Don't know

[If answer to 3. Is "No", then indicate answer "a" for question 5 and end telephone survey. If yes, then continue.]

- 4. Let's talk about the seizure that happened after you went home from the hospital. When did your child start having seizures?
 - a. Age_____ months
 - b. Don't know
- 5. How often does your child have a seizure now?
 - a. No seizures since he/she was a newborn
 - b. Seizure-free for at least 6 months (# of months seizure-free _____)
 - c. 1 12 seizures per year (Fewer than 1 seizure per month)
 - d. 1-4 seizures per month
 - e. 5-30 seizures per month
 - f. >30 seizures per month (daily seizures)
 - g. Multiple seizures a day (2 or more seizures per day)
 - h. Don't know
- 6. Has your child ever been diagnosed with infantile spasms (a particular kind of epilepsy)?
 - a. Yes
 - b. No
 - c. Don't know
- 7. Is your child taking medication for seizures now?
 - a. Yes (Name of medication(s), if known _____
 - b. No
 - c. Don't know

Epilepsy questions for medical record review:

- 1. Did the child remain seizure-free after discharge from the admission during which neonatal seizures were diagnosed?
 - a. Yes.
 - b. No. Acute symptomatic neonatal seizures stopped, but unprovoked seizures began later.
 i. Date of first unprovoked seizure:
 - c. No. Seizures persisted without a convalescent period.
 - d. Don't know.

2. Postneonatal seizure semiology:

- a. No seizures
- b. Seizure semiology:

	no	Yes, not specified	Bilateral, symmetric	Bilateral, asymmetric	Unilateral, focal	Unilateral, Hemi
Epileptic spasms						
Tonic						
Clonic						
Tonic Clonic						
Myoclonic-Tonic						
Myoclonic						
Myoclonic-Atonic						
Absence						
Atonic/Drop-attack						
Arrest/Staring/Blinking seizures						
Other Focal Motor						
Sensory/Autonomic						

- 3. Date of postneonatal epilepsy diagnosis:

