Possible biases due to differential loss to follow-up: It is possible that infants who are discharged from the initial hospital admission *without* anticonvulsant medication will be more likely to be lost to follow-up, since they will not need to present to a neurology clinic for prescription medication refills. In our clinical experience, however, these families want to return to clinic at least at the 2-4 month time point, so that a specialist can evaluate their child's growth and development. If a child is doing well, families who live farther from the study site may be less likely to follow-up at later time points. We have designed the assessment to avoid this problem by utilizing telephone interviews, online and mailed surveys. Even for families who do not complete the assessments, the medical chart can be reviewed. In cases where a family cannot be reached by telephone, a diagnosis of epilepsy will be readily apparent from electronic medical record review.

Data Safety and Security: Local Institutional Review Boards approvals for the *Neonatal Seizure Registry Sites* will be amended to reflect changes to the study design. Data will be collected using REDCap, an online, HIPAA compliant database that is designed for use in health care. Data will be de-identified, with each site maintaining local record of the patient medical record number in a secure manner (either on an encrypted and password protected computer that is maintained in a locked room, or paper file that is maintained in a locked cabinet in a locked room). Data that were collected for the *Neonatal Seizure Registry* prior to initiation of this proposal will be used only following informed consent from families.

Informed Consent: A study investigator will contact the parents/legal guardians of eligible patients and, using a consent form approved by the local Committee on Human Research (Institutional Review Board), describe the known risks and benefits of the study. The consent teams will include only experienced study personnel who are sensitive to the vulnerable nature of this population and who will emphasize the voluntary nature of research.

Data Quality Assurance

Data will be collected and entered into a REDCap database according to policies established for the *Neonatal Seizure Registry*.

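### The plan lets local record review stand in for the epilepsy call when a family is unreached, but has no rule for a child with little or no later record; coding such children negative would favour non-inferiority on Aim 1b

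*Combined protocol and SAP*

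**What the plan says.** Epilepsy (Aim 1b) is assessed by telephone at 12, 18 and 24 months. In Table 1 the chart has a supporting role: "epilepsy syndrome characteristics and treatment confirmed through medical record review".

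Appendix 6, under possible biases due to differential loss to follow-up, gives the chart a larger one. It accepts as a possibility that infants discharged without medication "will be more likely to be lost to follow-up, since they will not need to present to a neurology clinic". It then offers reassurance: "these families want to return to clinic at least at the 2-4 month time point", and telephone, online and mailed assessments avoid travel. It adds: "If a child is doing well, families who live farther from the study site may be less likely to follow-up at later time points". For families still unreached, the remedy is the chart: "In cases where a family cannot be reached by telephone, a diagnosis of epilepsy will be readily apparent from electronic medical record review".

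The record-review part of Appendix 4 asks "Did the child remain seizure-free after discharge from the admission during which neonatal seizures were diagnosed" and allows an answer of not known. Its later diagnosis item offers only the absence of postneonatal epilepsy or one of five named types.

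The Missing data section plans a complete-case primary analysis, compared with multiple imputation by chained equations, and a comparison of children lost and not lost. It does not say whether a child with chart review only is complete or missing for epilepsy.

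**The concern.** The reason given for loss in the short group, no need to attend a neurology clinic, is also a reason for the local record to be thin. Under barriers to recruitment, the protocol says that some "sites draw patients from significant geographical distances", so later care may be recorded elsewhere. The reassurance about returning to clinic reaches only 2–4 months of age, whereas the outcome is epilepsy by 24 months.

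An absent diagnosis can therefore mean either no epilepsy or not observed, and the diagnosis item cannot separate the two. Once such a child is entered as negative, complete-case analysis and multiple imputation both treat the value as observed, so comparing them would not reveal the problem.

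Under-counting in the short group lowers the difference that the non-inferiority test must bound. The Sample Size Calculations section says that, if development is similar, parents would accept prolonged medication in the hope of reducing epilepsy risk. Aim 1b can therefore decide the advice given.

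**Working it through.** **Inputs from the documents (Sample Size Calculations).** Epilepsy 20% in both groups; margin 13 points; one-sided 95% limit; 80% power; 90 short and 210 prolonged; 15% loss (45 of 300); 9% inflation for propensity adjustment.

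**The plan's own figure.** Detectable margin = (1.645 + 0.842) × √[0.2 × 0.8 × (1/n₁ + 1/n₂)]. Net N = 300 × 0.85 / 1.09 = 234. With equal arms of 117 this gives 13.0 points, the stated figure. With the planned split (70.2 and 163.8) it gives 14.2 points, and power at 13 points is 73.7%. That is a separate matter; 13 points is used below as the stated margin.

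**Assumptions, because the documents give no values.** Let u be the share of a group that is unreached and m the share of their true cases absent from the record. Unreached children are coded negative and stay in the denominator:

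observed rate = true rate × (1 − u × m)

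P(declare non-inferior) = Φ[(0.13 − observed difference)/SE − 1.645], with SE from the observed rates and 90 and 210 children. The error is this probability when the truth is 33% versus 20%.

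**One case in full: u = 15% in both groups, m = 0.5.** Short: 0.33 × (1 − 0.075) = 0.305. Prolonged: 0.20 × (1 − 0.075) = 0.185. Difference 0.120, SE 0.0554. (0.13 − 0.120)/0.0554 − 1.645 = −1.47, so the error is 7.1% instead of 5%.

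**Same m in both groups, total unreached held at 45.**

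| Unreached, short / prolonged | m | Bias if true rates are equal (points) | Error at true 13-point excess |
|---|---|---|---|
| 15% / 15% | 0.25 | 0 | 6.0% |
| 15% / 15% | 0.5 | 0 | 7.1% |
| 15% / 15% | 1 | 0 | 10.0% |
| 20% / 12.9% | 0.25 | −0.4 | 7.2% |
| 20% / 12.9% | 0.5 | −0.7 | 10.0% |
| 20% / 12.9% | 1 | −1.4 | 18.7% |
| 30% / 8.6% | 0.25 | −1.1 | 10.1% |
| 30% / 8.6% | 0.5 | −2.1 | 18.5% |
| 30% / 8.6% | 1 | −4.3 | 47.4% |

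**Record gap allowed to differ.** Take 15% of the prolonged group unreached with m = 0.2, and 20–30% of the short group unreached with m = 0.5–0.8. The bias at equal rates is −1.4 to −4.2 points and the error 12–39% (12–35% if 77 and 178 children are used). With m = 0.2 in both groups, the bias is −0.2 to −0.6 points and the error 6–8%.

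**Status set to missing instead.** If all unreached children are missing, and missing at random, the error stays at 5%. Power at 13 points is 76.8%, 75.5% and 72.4% for the three loss patterns, before the 9% adjustment, against 82.5% with all 300 observed.

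**A one-sided rule would bias the other way.** Suppose 20% / 12.9% are unreached, both true rates are 20%, and half the unreached cases appear in the chart. Keeping those cases while dropping the chart-only non-cases gives, for short, (14.4 + 1.8)/(72 + 1.8) = 22.0%, and for prolonged, (36.6 + 2.7)/(183 + 2.7) = 21.2%. Both rates are too high, and the difference is shifted by +0.8 points.

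**The case against.** A reader might infer that the plan counts an empty record as epilepsy-free. No text says so. The seizure-freedom item allows an answer of not known, the plan includes imputation and a comparison of lost with retained children, and Appendix 6 promises a retention plan defining loss to follow-up and a Manual of Operations with definitions. This objection stands: the negative coding is an inference from a missing rule. It does not dispose of the point, because the diagnosis item has no such answer and the available text does not say which item governs or how chart-only children enter the analysis.

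A reader might also infer that under-counting falls mainly on the short group. The plan calls higher loss there possible, no more. It links later loss to distance and to children doing well, and loss of that kind would mean fewer missed cases. The remark about distance concerns some sites and explains a travel stipend for the EEG. Calls at 12 and 18 months, alternate contacts, reminders and quarterly site reports all reduce the number of children with no information, and the plan places the highest epilepsy risk in the first year.

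Finally, the largest error figures need both higher loss and much emptier records in the short group, or every unreached case missed. They also assume that unreached children have the full group rate, and that a child with epilepsy is as likely as a healthy one to lack a local record. Both assumptions raise the estimate. These objections stand against the size. Some inflation remains with equal loss in both groups.

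**Conclusion.** The gap is real, and it affects the secondary outcome Aim 1b only; the chart fallback is not offered for the WIDEA FS. The plan relies on local records where its own reasoning suggests they may be thin, and it has no rule separating a true negative from an unobserved child.

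If such children are coded negative, the direction is anti-conservative. At a true 13-point excess the error rises from 5% to about 6–10% with equal or modest gaps. Less balanced assumptions give roughly 12–19%, and 35% or more appears only under extreme differential ones. These figures rest on assumed loss and record gaps. The documents do not support a statement that empty records are counted as epilepsy-free, that the short group is mainly affected, or that any one of these error rates is to be expected.

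**What to change.** - Record the date of the last completed call or clinical contact for every child, from the chart already being reviewed.
- Add an unknown or insufficient-record option to the diagnosis item in Appendix 4.
- Accept a negative 24-month status only with a completed call or a dated clinical contact in a defined 24-month window. Otherwise treat status as unknown after the last contact.
- Apply the rule to cases and non-cases alike: analyse time to epilepsy with censoring at last contact, or use the multiple imputation already planned. Do not use a complete-case analysis that keeps chart-found cases and drops chart-only non-cases.
- Report the source of ascertainment (call, chart only, unknown) by treatment group, and vary the assumed epilepsy rate among children of unknown status by group as a sensitivity analysis.

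The cost is SAP and form wording, one date field and one answer option, plus more missing or censored epilepsy outcomes, mainly in the short group. If 20–30% of that group were unreached and 50–80% of them had no adequate record, 10–24% of the group (9 to 22 of 90) would be affected. Precision falls accordingly. Censoring and imputation also assume that loss is unrelated to epilepsy given the measured data, which is why the sensitivity analysis is needed.
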